For Aim 2, an improved survival of the forearm placed catheter will be evaluated by functionality of catheter for intravenous therapy prior to patient discharge. The event is failure of functionality identified as inability to infuse without resistance during follow-up assessment during hospitalization. Duration of dwell and functional failure of the catheter will be employed to estimate catheter survival.

Specific Aim 3: To compare upper arm versus forearm extended dwell catheter placement for symptomatic catheter-related upper extremity venous thrombosis (CR-UEVT).

For Aim 3, we will measure incidence of all symptomatic CR-UEVT inclusive of superficial thrombophlebitis (SVT) and deep venous thrombosis (DVT) confirmed

UPPER ARM VS. FOREARM PLACEMENT OF EXTENDED DWELL CATHETERS: A COMPARATIVE EVALUATION OF BLOOD SAMPLING AND FUNCTIONALITY

by upper extremity venous duplex evaluation, to assess for a difference in thrombosis when an EDC is placed in the forearm compared to the upper arm.

Study Design

We propose a single-site, prospective two-arm randomized investigation of blood sampling and catheter survival of extended dwell catheters when site selection is evaluated. Specifically, EDC insertions in the forearm will be compared to upper arm insertions. The primary objective of this study is to demonstrate that blood sampling of the forearm (experimental group) is not inferior to blood sampling of the upper arm (control group). Exploratory secondary and adjusted multivariable analyses will also be conducted.

A single lumen, 20 gauge 8 cm EDC (BARD Powerglide STTM Midline Catheter) will be utilized for this evaluation.

We aim to recruit 96 patients with 48 in each arm to assess blood sampling functionality.

Study Population and Eligibility:

A cohort of clinicians are proficient in ultrasound-guided vascular access at our hospital. In the emergency department (ED), several physicians and nurses are competent in the procedure. On the inpatient side, the Vascular Access Team (VAT) at our hospital receives daily consults for patients that have advanced vascular access needs. This includes patients with prolonged vascular access needs and/or difficult vascular access patients. All inserters are trained to place a number of catheters with ultrasound-guidance: peripheral IVs, midlines, and EDCs.

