Investigators will perform a follow-up on the catheters daily while hospitalized. If qualified staff is not available, chart review will be performed on the first day staff returns back to the hospital. At each follow-up interval, the researcher notes the time of evaluation and assesses for blood sampling and functionality. At our institution, midlines and central lines can only be accessed for blood draws with a physician order. These instances are tracked in the medical record and will be recorded. The hospital policy for blood sampling follows Lippincott procedures for central venous access catheter blood sampling available at procedures.lww.com. If the qualified staff is able to aspirate blood from the catheter, blood sampling is considered intact. This sampling should be followed immediately by a 5-10 cc flush of saline to ensure no blood is visible in the tubing system. If blood does not readily aspirate, the line is flushed with 10 cc of saline and blood draw is re-attempted. If the catheter is unable to aspirate blood, the date and time of the failure of blood sampling is recorded. The presence or absence of blood within the lumen proximal to the hub is noted for occlusion for all VADs that cannot aspirate blood. After accessing the catheter, researchers are expected to flush and clean the catheter hub per institutional protocol for care and maintenance. All practitioners are given written instructions on this protocol. General functionality is also recorded if the VAD flushes with 5 ml of normal saline without resistance after the blood draw attempt. If the catheter cannot be flushed, the date and time of failure are recorded. If the catheter is identified to have failed prior to the follow-up assessment the date and time of failure and the reason for failure is obtained from chart review. If the patient is discharged prior to the time of follow-up assessment then the time of discharge is documented and the IV is presumed functional until time of discharge unless otherwise noted in the chart.

UPPER ARM VS. FOREARM PLACEMENT OF EXTENDED DWELL CATHETERS: A COMPARATIVE EVALUATION OF BLOOD SAMPLING AND FUNCTIONALITY

Sample Size and Statistical Analysis

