The sample size for the proposed work is based on the first aim since the other aims will use the same samples. We determined the sample size for the proposed study based on the assumption that upper extremity catheters have successful blood sampling 50% of the time and clinically acceptable practice of 75% success applies to the experimental arm. If there is a true difference in favor of the experimental group of 25%, then 48 patients are required to be 95% sure that the upper limit of a one-sided 95% confidence interval (or equivalently a 90% two-sided confidence interval) will exclude a difference in favor of the control or upper arm group of more than 20%. Considering dropout rate and early discharge, we doubled the sample size to 96 patients. When evaluating volumes of midline catheters placed at our institution, this is a feasible number of patients to recruit over 4-6 months.

Initial analyses will include descriptive statistics for all outcomes using means, standard deviations, and ranges for continuous measures, and frequencies and percentages for categorical measures. We will compare demographic and other potential confounding variables between arms using either Pearson's chi-square test (dichotomous variables such as gender) or a two-sample t-test (continuous variables such as age), as appropriate. Aims will be assessed using survival analysis with Kaplan-Meier curves, Pearson's chi-squared test, and logistic regression.

Site

William Beaumont Hospital, Royal Oak (RO) campus is a 1,100 bed major academic and referral center with Level 1 adult trauma and Level 2 pediatric trauma status. A major teaching facility, Beaumont, Royal Oak has 55 residency and fellowship programs with 454 residents and fellows. Beaumont is the exclusive clinical partner for the Oakland University William Beaumont School of Medicine. The Beaumont Research Institute was established more than 30 year ago at Royal Oak and offers research support services to clinical investigators.

Principal Investigator

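### Mean, SD and range are planned for every continuous outcome, but dwell time and time to blood-sampling failure are censored at discharge, so their raw means understate time to failure and shrink the arm difference

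*Combined protocol and SAP*

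**What the plan says.** All references are to the combined protocol and SAP.

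- **Sample Size and Statistical Analysis** opens the analysis with "descriptive statistics for all outcomes using means, standard deviations, and ranges for continuous measures". No exception is made for times that end without a failure, and no median is named.
- The same section then says "Aims will be assessed using survival analysis with Kaplan-Meier curves, Pearson's chi-squared test, and logistic regression". The three methods are not matched to individual aims, and no numerical summary of the Kaplan-Meier curve is specified.
- The two-sample t-test appears only for baseline comparisons: "We will compare demographic and other potential confounding variables between arms using either Pearson's chi-square test", with the t-test as the counterpart for continuous variables.
- **Specific Aim 2** defines the event within the hospital stay, "The event is failure of functionality identified as inability to infuse without resistance during follow-up assessment during hospitalization", and adds "Duration of dwell and functional failure of the catheter will be employed to estimate catheter survival".
- **Follow-up Assessment** gives the rule for a patient who leaves before the next check: "the IV is presumed functional until time of discharge unless otherwise noted in the chart". For Aim 1 it also records a time: "If the catheter is unable to aspirate blood, the date and time of the failure of blood sampling is recorded".
- On how common early discharge may be, the plan says only "Considering dropout rate and early discharge, we doubled the sample size to 96 patients".
- **Hypothesis/Objectives** states the hypothesis that forearm catheters survive longer, and an aim of quantifying the difference in catheter survival between the sites.

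**The concern.** Two of the quantities collected are continuous in form but are times to an event: dwell to functional failure, and time to loss of blood sampling. For a patient discharged with a working catheter, the recorded time is a lower bound on the failure time. Taken literally, the descriptive rule averages these lower bounds together with true failure times.

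Such a mean depends on how long patients stay as well as on how long catheters last. It is biased downward as an estimate of time to failure, and more so in the arm with better survival, because more of that arm's times are cut off. The arm difference is therefore compressed. An SD and range computed on the same values have the same defect; the maximum may simply be the longest stay.

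At stake is the numerical description of catheter survival. Mean and SD are the only summary in days that the plan prescribes, for an outcome on which it hypothesises a forearm advantage and promises to quantify it.

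**Working it through.** **Plan's own figures.** The plan gives no dwell time, length of stay or censoring rate, so there is none to reproduce for this point. Its sample size does reproduce. With success of 50% v 75%, a 20-point margin, one-sided alpha 0.05 and 95% power, n per arm = (1.645 + 1.645)² × (0.25 + 0.1875) / 0.45² = 23.4, rounded up to 24. That is 48 in total, doubled to 96. Only the resulting 48 per arm is used below.

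**Assumptions.** Failure times are exponential with mean m, and discharge times are independent and exponential with mean L, the same in both arms. Take m = 8 days (upper arm) and 16 days (forearm), a true ratio of 2.0, and L = 8 or 4 days. These values are illustrative.

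**Expected raw mean.** Observed dwell is the smaller of failure time and discharge time, with mean 1 / (1/m + 1/L). The expected censored fraction is (1/L) / (1/m + 1/L).

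| Mean stay L | Upper arm | Forearm | Apparent gain | Censored, upper v forearm |
|---|---|---|---|---|
| 8 days | 1/(1/8 + 1/8) = 4.0 | 1/(1/16 + 1/8) = 5.3 | 33% | 50% v 67% |
| 4 days | 1/(1/8 + 1/4) = 2.7 | 1/(1/16 + 1/4) = 3.2 | 20% | 67% v 80% |

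A true gain of 100%, or 8 days, appears as 1.3 days or 0.5 days.

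**Sensitivity to the assumed values.** With true means of 10 v 20 days, the expected raw means are 2.31 v 2.61 at mean stay 3, 3.33 v 4.00 at 5, 5.00 v 6.67 at 10, and 6.67 v 10.00 at 20. The true 10-day difference shrinks to between 0.30 and 3.33 days. With 10 v 15 days, the true 5-day difference shrinks to between 0.19 and 1.90. The exponential stay is not what drives the result: with a gamma-distributed stay (shape 4, mean 5 days) and 10 v 20 days, the raw means are 3.76 v 4.30.

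**Direction.** The mean of observed dwell is the integral over time of (probability not failed) × (probability not discharged). If the discharge pattern is the same in both arms, the arm with uniformly better survival has the longer expected observed dwell. Reversal in expectation needs unequal stays or crossing survival curves. With 10 v 20 days and a mean upper-arm stay of 5 days, the forearm stay would have to average below 1/(1/10 + 1/5 − 1/20) = 4.0 days.

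**Chance ranking.** In 20,000 simulated trials with 48 per arm, true means of 8 v 16 days and equal stays, the share in which the forearm ranks no better was:

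| Summary | Mean stay 8 | Mean stay 4 |
|---|---|---|
| Raw mean dwell | 8% | 19% |
| Failures per catheter-day | about 1% | about 4% |
| Kaplan-Meier restricted mean to day 7 | about 3% | 5% to 6% |

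**What the restricted mean estimates.** To day 7 it equals m × (1 − exp(−7/m)): 8 × (1 − exp(−7/8)) = 4.67 days and 16 × (1 − exp(−7/16)) = 5.67 days, a difference of 1.00 day. That target does not depend on L. It is smaller than the 8-day difference in full means because it counts only the first 7 days.

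**The case against.** The strongest reply is that the plan already analyses Aim 2 correctly. The sentence on the aims names Kaplan-Meier survival analysis. Aim 2 uses duration together with failure, which is what a Kaplan-Meier estimate requires. The discharge rule in Follow-up Assessment works as a censoring rule. The t-test is named for demographics and potential confounders only, and nothing makes mean dwell the Aim 2 estimate. All of this stands, and it limits the point to the descriptive summary.

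The descriptive sentence is also generic. It does not name dwell time or say that outcomes will be summarised by arm, and mean time in place is a legitimate description of exposure. This stands in part: the harm arises only if the mean is read as time to failure. But the sentence covers all outcomes without exception, and the plan offers no other figure in days.

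A reader might infer that the planned means would simply measure hospital stay. They would not. They mix stay and failure, and in the 8-day example half of the upper-arm times and a third of the forearm times are failures. A reader might also infer that the method reverses the arm difference. Under 1:1 randomisation with equal stays it does so only by chance, and some chance reversal remains with any alternative. Nor is dwell the only affected outcome, since time to sampling failure is cut off in the same way.

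Finally, heavy censoring is not documented. The doubling of the sample combines dropout and early discharge and states no rate.

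**Conclusion.** The point holds as a minor one. The stated descriptive rule does not suit dwell time or time to sampling failure. Applied to them, it understates time to failure and shrinks the difference between sites. In the main illustration, a doubling of mean time to failure appears as a gain of 20% to 33%, and the raw mean ranks the forearm no better in about 8% to 19% of trials, against about 1% to 4% for a failure rate per catheter-day and 3% to 6% for a day-7 restricted mean.

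These sizes rest on assumed failure and stay times, mainly exponential, with discharge independent of failure. The direction of the bias does not depend on the particular values; its size does. The failure rate's advantage also relies on a constant hazard, which the simulation satisfies by construction.

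The documents do not support saying that the Aim 2 comparison is invalid or that the primary non-inferiority objective is affected. What remains is an unsuitable summary together with a gap: the plan aims to quantify the survival difference but names no numerical Kaplan-Meier summary to do so.

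**What to change.** In Sample Size and Statistical Analysis, add a sentence exempting dwell time and time to blood-sampling failure from the mean, SD and range rule. For each, report by arm:

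- the numbers failed and censored, with reasons;
- Kaplan-Meier survival at fixed, pre-stated days;
- the Kaplan-Meier median, if reached.

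For dwell time, add the restricted mean to one pre-set day (day 7 is an example), with the between-arm difference and its 95% confidence interval. This provides the quantified survival difference that the objectives call for. If time in place is still wanted as a measure of exposure, label it as observed follow-up and not as catheter survival.

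The cost is a small SAP edit and routine software output, with no new data. The one drawback is that the horizon day must be fixed before the outcome data are examined. It should be a day to which follow-up in both arms is expected to extend.

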There is very limited research evaluating the impact of IV placement site on functionality or blood sampling ability. Only one small study of ultrasound-guided IV placements evaluated site in a prospective comparative fashion. The comparison was limited to evaluation of 56 patients in the "distal" or forearm group which comprised insertions in the antecubital/forearm area and 95 patients in the upper arm site. The authors concluded that "distal" placements have improved survival.¹¹ Further research is necessary to draw conclusions about EDCs and functionality/blood draws.

The potential value of forearm placements is especially relevant for patients with renal insufficiency. In the past three decades, there has been a significant increase in the patient population with chronic kidney disease. As the renal disease may progress and patients may require dialysis and establishment of an arteriovenous fistula, it is necessary to preserve the vasculature of the upper arm.¹²

UPPER ARM VS. FOREARM PLACEMENT OF EXTENDED DWELL CATHETERS: A COMPARATIVE EVALUATION OF BLOOD SAMPLING AND FUNCTIONALITY

In summary, there is a gap of knowledge on EDCs and blood draw ability regardless of site of insertion. While survival of EDCs has been evaluated, there is no literature that compares survival of upper arm to lower arm placement.

Hypothesis/Objectives:

We hypothesize the forearm is the favorable site for ultrasound-guided IV establishment in terms of survival. Placement of the catheter in the forearm to avoid antecubital fossa or muscle bellies of the upper arm reduces kinking and involves insertion in more shallow vessels and likely enhances survival of the catheter.

We hypothesize the forearm provides similar blood sampling functionality compared to upper arm insertion.

We aim to quantify the difference in blood draw ability and catheter survival, comparing placement of an extended dwell catheter in the upper arm to the forearm.

Specific Aims:

Specific Aim 1: To compare upper arm versus forearm extended dwell catheter placement for blood sampling functionality.

For Aim 1, blood sampling ability of the forearm compared to upper arm will be evaluated by daily blood draws prior to patient discharge. The event is failure to aspirate blood during follow-up assessment during hospitalization.

Specific Aim 2: To compare upper arm versus forearm extended dwell catheter placement for dwell time/survival of catheter.

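### Aim 1 is sized on a 20-point non-inferiority interval, but the sentence on how the aims will be assessed lists no method tied to that margin

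*Combined protocol and SAP*

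**What the plan says.** All references are to the combined protocol and SAP.

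- **Study Design.** The primary objective is "to demonstrate that blood sampling of the forearm (experimental group) is not inferior to blood sampling of the upper arm (control group"). The same paragraph adds: "Exploratory secondary and adjusted multivariable analyses will also be conducted".
- **Specific Aims, Aim 1.** The outcome is defined through its failure: "The event is failure to aspirate blood during follow-up assessment during hospitalization".
- **Sample Size and Statistical Analysis, first paragraph.** Success is assumed to be 50% in the upper arm and 75% in the forearm. With 48 patients, the limit of a one-sided 95% (two-sided 90%) interval "will exclude a difference in favor of the control or upper arm group of more than 20" percent. Then: "Considering dropout rate and early discharge, we doubled the sample size to 96 patients".
- **Sample Size and Statistical Analysis, second paragraph.** After descriptive statistics and baseline comparisons, one sentence covers all three aims: "Aims will be assessed using survival analysis with Kaplan-Meier curves, Pearson's chi-squared test, and logistic regression".
- **Follow-up Assessment.** On sampling failure: "If the catheter is unable to aspirate blood, the date and time of the failure of blood sampling is recorded". For a patient discharged before the assessment, "the IV is presumed functional until time of discharge unless otherwise noted in the chart".

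**The concern.** The margin and the 90% interval appear only as the basis for the sample size. The sentence that says what will be done with the data mentions no margin, no interval for a difference and no non-inferiority test. It also does not say which of the three methods is primary for Aim 1.

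None of the three, as listed, answers the primary question:

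- Pearson's chi-squared tests whether the difference is zero. A large p-value does not rule out a 20-point deficit, and a small one is not needed to rule it out.
- Kaplan-Meier curves could give a difference to set against 20 points, but only at a stated time, and none is stated.
- A logistic model with arm as its only term could return the two success proportions, but the plan does not connect it to the margin.

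An analyst who carried out that sentence and nothing more would not have tested the primary objective.

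**Working it through.** **Inputs.** From the sample-size paragraph: upper arm p_U = 0.50, forearm p_F = 0.75, margin M = 0.20 (read as absolute), one-sided 5%, and 95% for the chance of success. Allocation is 1:1 (Initial Assessment). Assumed here: 48 evaluable per arm (no losses) and a two-sided 5% level for chi-squared, since the plan gives neither.

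**1. The plan's own figure.**

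n per arm = (z₀.₉₅ + z₀.₉₅)² × [p_F(1 − p_F) + p_U(1 − p_U)] / (p_F − p_U + M)²

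= (1.645 + 1.645)² × (0.1875 + 0.25) / 0.45² = 10.82 × 0.4375 / 0.2025 = 23.4, so 24 per arm.

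That is 48 in total, as stated, and 96 (48 per arm) after doubling. The figure therefore belongs to a margin-based comparison of two proportions.

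**2. Power of the two analyses at 75% versus 50%.**

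- SE = √(0.4375/n), which is 0.0955 at n = 48.
- Interval rule: Φ(0.45/SE − 1.645) = Φ(3.07) = 99.9%.
- Chi-squared: SE₀ = √(2 × 0.625 × 0.375/48) = 0.0988. Power = Φ((0.25 − 1.96 × 0.0988)/0.0955) = Φ(0.59) = 72%.

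With 24 per arm, the number before doubling, the same formulas give 95.4% and about 43%. For 95% power, chi-squared would need 95 per arm.

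**3. Same chi-squared reading, opposite non-inferiority results.** Forearm minus upper arm, 48 per arm, 90% Wald interval, uncorrected chi-squared:

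| Forearm | Upper arm | Difference (points) | 90% CI (points) | Chi-squared p | Lower limit above −20? |
|---|---|---|---|---|---|
| 22/48 | 24/48 | −4.2 | −20.9 to +12.6 | 0.68 | No |
| 30/48 | 24/48 | +12.5 | −4.0 to +29.0 | 0.22 | Yes |

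Both tests are non-significant. Only the interval separates the two results.

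**4. How often the answers differ.** Exact enumeration of two independent binomials, 90% Newcombe interval, uncorrected chi-squared. The last column is the probability that p > 0.05 and the lower limit is at or below −20 points:

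| True forearm vs upper arm | n per arm | Probability |
|---|---|---|
| 50% vs 50% | 48 | 35.2% |
| 75% vs 50% | 48 | 0.1% |
| 75% vs 50% | 36 | 0.8% |
| 75% vs 50% | 24 | 4.6% |

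**5. Check of the interval rule.** At a true 30% versus 50%, exactly on the margin, with 48 per arm, the rule accepts non-inferiority in 5.3% of trials by Newcombe and 4.7% by Wald. Both are close to the nominal 5%, so either method can be named.

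**The case against.** The strongest reply is that the decision rule is already in the document. Study Design fixes the hypothesis and the experimental arm. The sizing paragraph, under a heading that covers both sample size and analysis, fixes the measure, interval, margin and direction. A non-inferiority claim based on chi-squared would contradict that criterion. This stands: what is missing is the sentence that carries the criterion into the analysis. A reader might infer that the plan has no criterion, or that the method is free to be chosen after the data are seen. The documents do not support that much.

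A reader might also infer that a non-significant chi-squared would be reported as similarity. On that reading a true 30% versus 50% would be accepted in about 48% of trials with 48 per arm. The plan nowhere says this, so the 48% is not an error rate of the plan.

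Nor can logistic regression be set aside because Study Design calls adjusted multivariable analyses exploratory. The analysis sentence does not say that the model is adjusted, and a model with arm alone is not multivariable.

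Finally, under the plan's own 75% versus 50% the discrepancy in step 4 is only 0.1% with 48 per arm. That is true. However, the Hypothesis section expects similar blood sampling in the two sites, and that is where the two approaches part.

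**Conclusion.** The point holds as a mismatch between design and analysis. The primary objective and the sample size rest on a 20-point margin, and the only sentence on assessing the aims does not use it. The sample size itself reproduces and is not in question.

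Assuming 48 evaluable per arm and a two-sided 5% chi-squared test, power at 75% versus 50% is 99.9% for the interval rule and about 72% for chi-squared. If both arms are truly 50%, the two give differing answers of the kind in step 4 in 35% of trials. They answer different questions, so this is not an error rate.

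A secondary gap concerns the outcome. The presumption of function until discharge does not say whether it covers blood sampling when there was no follow-up draw. Follow-up Assessment records sampling and flushing separately, while Initial Assessment uses functionality to cover both. A reader might infer that this gap will reverse the result. The documents give no share of such patients, so its size cannot be stated. It calls for one clarifying sentence and a sensitivity analysis.

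**What to change.** Add to the second paragraph of Sample Size and Statistical Analysis:

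> The primary analysis of Aim 1 is the forearm minus upper-arm difference in the proportion of patients with successful blood sampling (no Aim 1 event as defined under Specific Aims), by randomized arm, with a two-sided 90% confidence interval by [Newcombe or Wald, to be named]. Non-inferiority is concluded only if the lower limit is above −20 percentage points. Chi-squared, Kaplan-Meier and logistic regression are supporting. A non-significant difference test is not evidence of non-inferiority.

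Also:

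- Repeat the interval by site actually used, because Study Population and Initial Assessment allow insertion at another site. Report any disagreement with the conclusion.
- Report a Kaplan-Meier difference at a pre-stated time beside the proportion.
- State whether the presumption of function until discharge applies to blood sampling when there was no follow-up draw, and report the other handling as a sensitivity analysis.

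**Cost.** Wording and a few intervals from data already planned, including the recorded time of sampling failure. N is unchanged.

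**Downsides**, with 48 per arm and Newcombe intervals; the switching and stay patterns are assumptions:

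- *Site switching dilutes the randomized comparison.* With a true 30% versus 50% by site used, 10% switching in each arm gives 0.9 × 30 + 0.1 × 50 = 32% versus 0.9 × 50 + 0.1 × 30 = 48%, and the rule accepts in about 11% of trials. At 20% switching (34% versus 46%) it accepts in about 21%. Hence the analysis by site used.
- *Short stays dilute a simple proportion.* Take day-5 success of 30% versus 50% at constant daily risk. If a quarter of patients leave after one assessed day, the difference shrinks to −17.1 points and the rule accepts in about 8% of trials. If half do, it shrinks to −14.2 points and the rule accepts in about 16%. Hence the Kaplan-Meier difference.

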After patient enrollment, the inserter is engaged to perform the procedure. Only providers that are credentialed in ultrasound-guided vascular access will place catheters in study subjects. The research team will capture and save images of vessel depth and vessel diameter in short axis using the Sonosite or Mindray ultrasound equipment. Ultrasound guidance will be used for the initial assessment and procedure. The high frequency linear array transducer will be used for all procedures. Inserters will evaluate the vessel for valves, thrombosis, trajectory, and collapsibility per routine care. If the vein is appropriate for cannulation, the practitioner will continue with the procedure. Post-cannulation and post securement, functionality is confirmed with blood sampling (10 cc) and flush without resistance. A neutral pressure needle-free IV connector (One-link by Baxter Medical) will be connected to all lines. If the patient is randomized to the control group, the research staff will direct the inserter to choose either the basilic, cephalic or brachial vein at least 2 cm above the antecubital fossa. If the patient is randomized to the experimental group, the research staff will direct the inserter to place the catheter into the forearm at least 10 cm away from the antecubital fossa to ensure the distal tip of the catheter does not terminate in the antecubital fossa. The cephalic and basilic veins are typically cannulated in the forearm. If no adequate target is visualized in the randomly selected site, the inserter may evaluate another

UPPER ARM VS. FOREARM PLACEMENT OF EXTENDED DWELL CATHETERS: A COMPARATIVE EVALUATION OF BLOOD SAMPLING AND FUNCTIONALITY

site that is more suitable for cannulation. The site of insertion will be recorded and pertinent information will be collected similar to other enrollments.

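### Does the plan leave Aim 2 (catheter survival) without a proper between-arm comparison because it names no log-rank test or hazard model?

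*Combined protocol and SAP*

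**What the plan says.** Specific Aims sets Aim 2 as "To compare upper arm versus forearm extended dwell catheter placement for dwell time/survival of catheter". Its event is defined thus: "The event is failure of functionality identified as inability to infuse without resistance during follow-up assessment during hospitalization". The endpoint combines time and status: "Duration of dwell and functional failure of the catheter will be employed to estimate catheter survival".

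Follow-up Assessment has catheters checked daily in hospital, with the date and time of any failure recorded. For a patient who leaves before a check, the discharge time is noted and "the IV is presumed functional until time of discharge unless otherwise noted in the chart".

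Sample Size and Statistical Analysis gives the methods for all three aims in one sentence: "Aims will be assessed using survival analysis with Kaplan-Meier curves, Pearson's chi-squared test, and logistic regression". Study Design adds, without naming a model: "Exploratory secondary and adjusted multivariable analyses will also be conducted". Study Design also makes non-inferiority of blood sampling (Aim 1) the primary objective, and the sample size rests on Aim 1 alone.

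Two further places bear on Aim 1. In Initial Assessment, after placement, "functionality is confirmed with blood sampling (10 cc) and flush without resistance". In the sample size paragraph: "Considering dropout rate and early discharge, we doubled the sample size to 96 patients".

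**The concern.** Aim 2 yields right-censored data: follow-up ends at discharge, which varies by patient. Kaplan-Meier curves estimate survival in each arm but do not test the difference. The only between-arm test and model named for the aims are chi-squared and logistic regression. Applied to Aim 2, they would treat a catheter working at discharge on day 1 like one that worked for many days. The stake would be lost power for the hypothesised forearm advantage and, if time at risk differed by arm, false positives.

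A second doubt concerns the primary comparison. Initial Assessment confirms functionality by both sampling and flush. If the assumption that an unchecked line works until discharge also covered sampling, patients never tested would enter Aim 1 as successes and draw the arms together, which favours a non-inferiority claim.

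**Working it through.** **1. The plan's own figure.** Inputs from Sample Size and Statistical Analysis: success 50% (upper arm) and 75% (forearm), margin 20 points, one-sided 5%, 95% power. Per arm, n = (1.645 + 1.645)² × (0.50×0.50 + 0.75×0.25) / (0.25 + 0.20)² = 10.82 × 0.4375 / 0.2025 = 23.4, so 24 per arm and 48 in total, as stated. Doubling gives 96, or 48 per arm. No figure is given for Aim 2, so nothing in the sample size depends on its test.

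**2. Which method fits which aim.** Aim 2 is the aim defined by duration. Aim 1 is sized as a comparison of proportions, and Aim 3 is an incidence of thrombosis. Survival analysis therefore fits Aim 2, and chi-squared and logistic regression fit Aims 1 and 3. No sentence assigns chi-squared to Aim 2.

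**3. Cost if chi-squared were used for Aim 2 anyway.** The documents give no failure or discharge rates, so every rate here is assumed: exponential failure (rate λ) and discharge (rate c), 48 per arm, two-sided 5%, hazard ratio 0.5, 40,000 simulated trials per row.

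| Failure per day | Discharge per day | Log-rank power | Chi-squared power | Difference (points) |
|---|---|---|---|---|
| 0.15 v 0.075 | 0.05 | 78.3% | 35.5% | 42.8 |
| 0.15 v 0.075 | 0.15 | 56.8% | 38.3% | 18.5 |
| 0.15 v 0.075 | 0.3 | 39.4% | 31.9% | 7.5 |
| 0.15 v 0.075 | 0.5 | 27.8% | 25.3% | 2.5 |
| 0.06 v 0.03 | 0.05 | 61.4% | 39.8% | 21.6 |
| 0.06 v 0.03 | 0.15 | 33.9% | 28.4% | 5.5 |
| 0.06 v 0.03 | 0.3 | 21.1% | 21.3% | −0.2 |
| 0.06 v 0.03 | 0.5 | 14.4% | 16.5% | −2.1 |

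Hand check of the first row. The crude failure proportion is λ/(λ + c): 0.15/0.20 = 0.75 and 0.075/0.125 = 0.60.
- Chi-squared: pooled proportion 0.675; (0.15 − 1.96 × √(2×0.675×0.325/48)) / √((0.1875 + 0.24)/48) = (0.15 − 0.187)/0.094 = −0.40, so power is about 35%.
- Log-rank: expected events 48 × (0.75 + 0.60) = 64.8; √64.8/2 × ln 2 − 1.96 = 2.79 − 1.96 = 0.83, so power is about 80%.

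Both agree with the simulation to within the approximation. Detecting failures only at the next daily check changes little (76.8% v 33.3% in that row; 20,000 trials).

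**4. False positives.** With equal hazards and equal stays, log-rank rejects in 4.9 to 5.3% of trials and chi-squared in 5.0 to 5.4%. With equal hazards of 0.1/day but mean stays of 5 v 3 days, crude failure is 0.1/0.3 = 33% v 0.1/0.433 = 23%; chi-squared rejects in 20.2% and log-rank in 5.1%. At 5 v 4 days the figures are 8.1% and 5.2%. Allocation is randomised 1:1, and the documents give no reason why catheter site should change length of stay.

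**5. Aim 1.** Take the boundary case, true success 50% v 30%, with a share f untested in each arm and missingness unrelated to outcome. The figures are exact probabilities that the 90% Wald interval excludes 20 points.
- Counted as successes, p′ = p(1 − f) + f. At f = 0.2 this is 60% v 44%, a 16-point gap. False non-inferiority is 4.7/7.0/10.1/14.1% at f = 0/10/20/30%.
- Excluded (48/43/38/34 per arm): 4.7/5.4/4.8/5.7%.

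Exclusion is affordable. At 30% untested, 48 × 0.7 = 33.6, about 34 per arm, against the 24 required; power at the plan's 50% v 75% is 99.0%.

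Follow-up Assessment records aspiration and flushing as separate items and ties general functionality to the saline flush. The assumption about unchecked lines therefore reads most naturally as an Aim 2 rule. The doubling for dropout and early discharge suggests that such patients are treated as lost. A patient tested on earlier days already has a sampling result, so the never-tested share may be well below the values used here.

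**The case for a change.** The strongest case for a change is that survival analysis is only a label and Kaplan-Meier only an estimator. Neither fixes a test, an effect measure or an adjusted model, so the choice could be made after seeing the data. Better forearm survival is a stated hypothesis, Aim 2 has no sample size of its own, and logistic regression is the only model named for the adjusted analyses. A sentence or two would close the gap, using data already collected.

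The literal point stands: no between-arm time-to-event method is named anywhere. So does the power loss if chi-squared were used with long stays. The step from that to a flawed plan does not stand, because each quantified harm for Aim 2 requires an analyst to pass over the survival analysis the plan names, on an aim that is not the primary objective.

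Nor is extra wording free of risk. Censoring every working catheter at discharge would overlook those removed earlier. With assumed failure and discharge both at 0.1/day and removal of working catheters at 0.1 v 0.3/day, that rule gives about 29% false positives, against 5% if censored at removal. For Aim 1, a rule that untested patients are not successes could be read as making them failures, which gives 7.5/11.5/16.7% false non-inferiority at 10/20/30% untested. That is slightly worse than counting them as successes.

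**Conclusion.** The concern does not call for a change. The methods sentence is short on detail, but it names the right family of methods for Aim 2, the endpoint is defined as time plus failure, and the times needed are recorded. A competent analyst would add the log-rank test and, for adjustment, a hazard model.

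If chi-squared were used instead, the expected cost would be power: 43 points in the most adverse assumed setting, under 8 points in five of the eight settings, and a slight gain in two of those five. Type I error stays near 5% unless time at risk differs between arms.

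The Aim 1 doubt would matter only if untested patients were entered as successes, and the separate recording of sampling and flushing points away from that reading.

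These sizes rest on assumed exponential failure and discharge rates, 48 evaluable per arm for Aim 2, and for Aim 1 on missingness unrelated to outcome. The conclusion rests on the text: nothing in it directs chi-squared or logistic regression to Aim 2.
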